10.1 Compliance with Financial Disclosure Requirements

Financial Disclosure requirements are outlined in the US Food and Drug Administration Regulations, Financial Disclosure by Clinical Investigators (21 CFR Part 54). It is the Sponsor's responsibility to determine, based on these regulations, whether a request for Financial Disclosure information is required. It is the investigator's/subinvestigator's responsibility to comply with any such request.

The investigator/subinvestigator(s) agree, if requested by the Sponsor in accordance with 21 CFR Part 54, to provide his/her financial interests in and/or arrangements with the Sponsor to allow for the submission of complete and accurate certification and disclosure statements. The investigator/subinvestigator(s) further agree to provide this information on a Certification/Disclosure Form, commonly known as a financial disclosure form, provided by the Sponsor. The investigator/subinvestigator(s) also consent to the transmission of this information to the Sponsor in the United States for these purposes. This may involve the transmission of information to countries that do not have laws protecting personal data.

10.2 Compliance with Law, Audit and Debarment

The investigator agrees to conduct the trial in an efficient and diligent manner and in conformance with this protocol; generally accepted standards of Good Clinical Practice (e.g., International Conference on Harmonization of Technical Requirements for Registration of Pharmaceuticals for Human Use Good Clinical Practice: Consolidated Guideline and other generally accepted standards of good clinical practice); and all applicable federal, state and local laws, rules and regulations relating to the conduct of the clinical trial.

The investigator also agrees to allow monitoring, audits, IRB review and regulatory authority inspection of trial-related documents and procedures and provide for direct access to all trial-related source data and documents.

The investigator agrees not to seek reimbursement from subjects, their insurance providers or from government programs for procedures included as part of the trial reimbursed to the investigator by the Sponsor.

The investigator shall prepare and maintain complete and accurate trial documentation in compliance with Good Clinical Practice standards and applicable federal, state and local laws, rules and regulations; and, for each subject participating in the trial, provide all data, and, upon completion or termination of the clinical trial, submit any other reports to the Sponsor as required by this protocol or as otherwise required pursuant to any agreement with the Sponsor.

Trial documentation will be promptly and fully disclosed to the Sponsor by the investigator upon request and also shall be made available at the trial site upon request for inspection, copying, review and audit at reasonable times by representatives of the Sponsor or any regulatory authorities. The investigator agrees to promptly take any reasonable steps that are requested by the Sponsor as a result of an audit to cure deficiencies in the trial documentation and worksheets/case report forms.

The investigator must maintain copies of all documentation and records relating to the conduct of the trial in compliance with all applicable legal and regulatory requirements. This documentation includes, but is not limited to, the protocol, worksheets/case report forms, advertising for subject participation, adverse

event reports, subject source data, correspondence with regulatory authorities and IRBs/ERCs, consent forms, investigator's curricula vitae, monitor visit logs, laboratory reference ranges, laboratory certification or quality control procedures and laboratory director curriculum vitae. The investigator agrees that documentation shall be retained until at least 2 years after the last approval of a marketing application in an ICH region or until there are no pending or contemplated marketing applications in an ICH region or until at least 2 years have elapsed since the formal discontinuation of clinical development of the investigational product.

Because the clinical development and marketing application process is variable, it is anticipated that the retention period can be up to 15 years or longer after protocol database lock. The Sponsor will determine the minimum retention period and notify the investigator when documents may be destroyed. The Sponsor will determine the minimum retention period and upon request, will provide guidance to the investigator when documents no longer need to be retained. The sponsor also recognizes that documents may need to be retained for a longer period if required by local regulatory requirements. All trial documents shall be made available if required by relevant regulatory authorities. The investigator must consult with and obtain written approval by the Sponsor prior to destroying trial and/or subject files.

ICH Good Clinical Practice guidelines recommend that the investigator inform the subject's primary physician about the subject's participation in the trial if the subject has a primary physician and if the subject agrees to the primary physician being informed.

The investigator will promptly inform the Sponsor of any regulatory authority inspection conducted for this trial.

Persons debarred from conducting or working on clinical trials by any court or regulatory authority will not be allowed to conduct or work on this Sponsor's trials. The investigator will immediately disclose in writing to the Sponsor if any person who is involved in conducting the trial is debarred or if any proceeding for debarment is pending or, to the best of the investigator's knowledge, threatened.

In the event the Sponsor prematurely terminates a particular trial site, the Sponsor will promptly notify that trial site's IRB.

11.0 Compliance with Trial Registration and Results Posting Requirements

Under the terms of the Food and Drug Administration Modernization Act (FDAMA) and the Food and Drug Administration Amendments Act (FDAAA), the Sponsor of the trial is solely responsible for determining whether the trial and its results are subject to the requirements for submission to the Clinical Trials Data Bank, <http://www.clinicaltrials.gov>. Information posted will allow subjects to identify potentially appropriate trials for their disease conditions and pursue participation by calling a central contact number for further information on appropriate trial locations and trial site contact information.

The Sponsor agrees to be responsible for implementing and maintaining a quality management system with written development procedures and functional area standard operating procedures (SOPs) to ensure that trials are conducted and data are generated, documented, and reported in compliance with the protocol, accepted standards of Good Clinical Practice, and all applicable federal, state, and local laws, rules and regulations relating to the conduct of the clinical trial.

The Quality Assurance (QA) division in the Miami Cancer Institute Office of Clinical Research (MCI OCR) is responsible for ensuring that industry standards of quality are met and exceeded on an on-going basis. The division is responsible for the identification, management, and prevention of quality issues, reviewing subject research charts, and mapping out current processes. They develop and implement quality and verification checks, including necessary assessment tools and checklists used during the QC process. Moreover, they facilitate and advise on corrections and corrective and preventive actions related to quality issues, provide guidance on interpretation and application of regulations, manage FDA and sponsor site visits, and work with site manager to create, implement, and evaluate action plans.

12.0 DATA MANAGEMENT

The Miami Cancer Institute Office of Clinical Research (MCI OCR) oversees record keeping and handling of data is to record, store, transfer and, where necessary, convert efficiently and accurately, the information gathered on each trial subject into data.

All steps involved in data management should be documented in order to allow step-by-step retrospective assessment of quality of the data and the performance of the clinical trial (the “audit paper trail” concept). Documentation is facilitated by methods such as the use of checklists and forms giving details of action taken, dates, the individuals responsible, etc.

In the event of electronic data handling, confidentiality of the database must be secured by safety procedures such as passwords and written assurances from all staff involved. Provision must be made for the satisfactory maintenance of the database and for back-up procedures.

12.1 Responsibilities of the investigator

- a) The investigator has overall responsibility for ensuring the accuracy and completeness of data entry. The investigator must ensure that the observations and findings are recorded correctly and completely in the case-report forms (CRFs) and signed by the responsible person designated in the protocol. When conducting a study and using CRFs to report clinical trial data to the sponsor, the investigator must also ensure that the routine requirements for recording of data in the source documents (e.g. hospital and laboratory records, consultation files) are met, particularly those relating to the treatment given to the subject and adverse events.
- b) If trial data are entered directly into a computer, there must always be an adequate safeguard to ensure validation, including a signed and dated print-out and back-up records. Computerized systems should be validated and a detailed description for their use be produced and kept up-to-date.
- c) All corrections to CRFs and to raw data must be made in a way which does not obscure the original entry. The correct data must be inserted with the reason for the correction (if not obvious), the date, and the initials of the investigator or authorized person. For electronic data processing, only authorized persons should be permitted to enter or modify data in the computer and there should be a record of changes and deletions. If data are altered during processing, the alteration must be documented.
- d) Laboratory values with normal reference ranges, preferably together with the specificity and sensitivity of the methods used, should always be recorded on the CRF or be attached to it. Values outside a clinically accepted reference range or values that differ significantly from previous values must be evaluated and commented upon by the investigator.

- e) Data other than those required by the protocol may appear on the CRF, provided they are clearly marked as additional or optional findings, with an explanation of their significance.
- f) Units of measurement must always be stated, and conversion of units must always be indicated and documented.
- g) The final report of the trial should be drawn up as defined in the protocol. The report should be signed by the sponsor, monitor and investigator(s) as well as the responsible statistician, in accordance with the applicable regulations.
- h) For a period of time defined by national regulations, the investigator should maintain a confidential record to allow the translation of the unambiguous code used to conceal the identity of the individual subjects in the trial (subject identification code). The investigator may submit the subject identification code list to the drug regulatory authority after the trial, together with the final report, according to national regulations.
- i) The investigator should ensure that the subject's participation in the clinical trial is clearly marked in his or her medical records.

14.0 APPENDICES

Appendix 1: ECOG Performance Status

Grade	Description
0	Normal activity. Fully active, able to carry on all pre-disease performance without restriction.
1	Symptoms, but ambulatory. Restricted in physically strenuous activity, but ambulatory and able to carry out work of a light or sedentary nature (e.g., light housework, office work).
2	In bed <50% of the time. Ambulatory and capable of all self-care, but unable to carry out any work activities. Up and about more than 50% of waking hours.
3	In bed >50% of the time. Capable of only limited self-care, confined to bed or chair more than 50% of waking hours.
4	100% bedridden. Completely disabled. Cannot carry on any self-care. Totally confined to bed or chair.
5	Dead.

*As published in Am. J. Clin. Oncol.: *Oken, M.M., Creech, R.H., Tormey, D.C., Horton, J., Davis, T.E., McFadden, E.T., Carbone, P.P.: Toxicity And Response Criteria Of The Eastern Cooperative Oncology Group. Am J Clin Oncol 5:649-655, 1982.* The Eastern Cooperative Oncology Group, Robert Comis M.D., Group Chair.

Appendix 2: Common Terminology Criteria for Adverse Events V5.0 (CTCAE)

The descriptions and grading scales found in the revised NCI Common Terminology Criteria for Adverse Events (CTCAE) version 5.0 will be utilized for adverse event reporting. (<http://ctep.cancer.gov/reporting/ctc.html>)

For each episode of an adverse event, all changes to the CTCAE grade attained as well as the highest attained CTC grade should be reported.

Appendix 3: Contraceptive Guidance and Pregnancy Testing

Woman of Childbearing Potential (WOCBP)

A woman is considered fertile following menarche and until becoming post-menopausal unless permanently sterile (see below)

Women in the following categories are not considered WOCBP:

- Premenarchal
- Premenopausal female with 1 of the following:
 - Documented hysterectomy
 - Documented bilateral salpingectomy
 - Documented bilateral oophorectomy

Note: Documentation can come from the site personnel's review of the participant's medical records, medical examination, or medical history interview.

- Postmenopausal female
 - A postmenopausal state is defined as no menses for 12 months without an alternative medical cause.
 - A high follicle stimulating hormone (FSH) level in the postmenopausal range may be used to confirm a postmenopausal state in women not using hormonal contraception or hormonal replacement therapy (HRT). However, in the absence of 12 months of amenorrhea, confirmation with two FSH measurements in the postmenopausal range is required.

Postmenopausal is defined as:

- Amenorrheic for 1 year or more following cessation of exogenous hormonal treatments
- Luteinizing hormone (LH) and Follicle stimulating hormone (FSH) levels in the post-menopausal range for women under 50
- radiation-induced oophorectomy with last menses >1 year ago
- chemotherapy-induced menopause with >1 year interval since last menses
- surgical sterilisation (bilateral oophorectomy or hysterectomy)

- Females on HRT and whose menopausal status is in doubt will be required to use one of the non-hormonal highly effective contraception methods if they wish to continue their HRT during the study. Otherwise, they must discontinue HRT to allow confirmation of postmenopausal status before study enrollment.

Contraception Requirements

Female Participants:

Female participants of childbearing potential are eligible to participate if they agree to use a highly effective method of contraception that has a low user dependency consistently and correctly as described in Table 9 during the protocol-defined time frame.

Acceptable Birth Control Methods

Olaparib is regarded as a compound with medium/high fetal risk.

Women of childbearing potential and their partners, who are sexually active, must agree to the use of TWO highly effective forms of contraception in combination [as listed below]. This should be started from the signing of the informed consent and continue throughout the period of taking study treatment and for at least 1 month after last dose of study drug(s), or they must totally/truly abstain from any form of sexual intercourse (see below).

Acceptable Non-hormonal birth control methods include:

- Total/True abstinence: When the patient refrains from any form of sexual intercourse and this is in line with their usual and/or preferred lifestyle; this must continue for the total duration of the trial and for at least 1 month after the last dose of study drug. [Periodic abstinence (e.g., calendar, ovulation, symptothermal, post-ovulation methods, or declaration of abstinence solely for the duration of a trial) and withdrawal are not acceptable methods of contraception]
- Vasectomised sexual partner PLUS male condom. With participant assurance that partner received post-vasectomy confirmation of azoospermia.
- Tubal occlusion PLUS male condom
- IUD PLUS male condom. Provided coils are copper-banded

Acceptable hormonal methods:

- Normal and low dose combined oral pills PLUS male condom
- Cerazette (desogestrel) PLUS male condom. Cerazette is currently the only highly efficacious progesterone based pill.
- Hormonal shot or injection (eg., Depo-Provera) PLUS male condom
- Etonogestrel implants (e.g., Implanon, Norplant) PLUS male condom
- Norelgestromin / EE transdermal system PLUS male condom
- Intrauterine system [IUS] device (eg., levonorgestrel releasing IUS -Mirena®) PLUS male condom
- Intravaginal device (e.g., EE and etonogestrel) PLUS male condom

Table 16 Highly-Effective Contraceptive Methods That Have Low User Dependency

Highly Effective Methods That Have Low User Dependency Failure rate of <1% per year when used consistently and correctly.

 • Progestogen- only contraceptive implant ^{a, b} • Intrauterine hormone-releasing system (IUS) ^b • Intrauterine device (IUD) • Bilateral tubal occlusion


● Vasectomized partner A vasectomized partner is a highly effective contraception method provided that the partner is the sole male sexual partner of the WOCBP and the absence of sperm has been confirmed. If not, an additional highly effective method of contraception should be used.● Sexual abstinence Sexual abstinence is considered a highly effective method only if defined as refraining from heterosexual intercourse during the entire period of risk associated with the study treatment. The reliability of sexual abstinence needs to be evaluated in relation to the duration of the study and the preferred and usual lifestyle of the participant.

Notes:
 
Use should be consistent with local regulations regarding the use of contraceptive methods for participants of clinical studies.
 
a) If locally required, in accordance with Clinical Trial Facilitation Group (CTFG) guidelines, acceptable contraceptive implants are limited to those which inhibit ovulation.
 
b) If hormonal contraception efficacy is potentially decreased due to interaction with study treatment, condoms must be used in addition to the hormonal contraception during the treatment period and for at least [X days, corresponding to time needed to eliminate study treatment plus 30 days for study treatments with genotoxic potential] after the last dose of study treatment.

Pregnancy Testing

WOCBP should only be included after a negative highly sensitive urine or serum pregnancy test.

Pregnancy testing will be performed whenever an expected menstrual cycle is missed or when pregnancy is otherwise suspected.

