5.1.1 Participant Inclusion Criteria

Participants are eligible to be included in the study only if all of the following criteria apply:

1. Female participants who are at least 18 years of age on the day of signing informed consent with histologically confirmed diagnosis of cervical carcinoma will be enrolled in this study.
2. Cervical cancer is a disease of the female genital tract. No male patients will be enrolled.
3. A female participant is eligible to participate if she is not pregnant (see Appendix 3), not breastfeeding, and at least one of the following conditions applies:
 - a. Not a woman of childbearing potential (WOCBP) as defined in Appendix 3
OR
 - b. A WOCBP who agrees to follow the contraceptive guidance in Appendix 3 during the treatment period and for at least 120 days after the last dose of study treatment.
4. Participant must have recurrent cervical cancer and have a low potential for cure with radiation therapy or surgery alone and:
 - a. May have received up to 2 prior chemotherapy regimens. Platinum sensitizing agents for radiation therapy are considered a chemotherapy regimen.
5. The participant (or legally acceptable representative if applicable) provides written informed consent for the trial, which includes compliance with the requirements and restrictions listed in the informed consent form (ICF) and this protocol.
6. Have measurable disease based on RECIST 1.1. Lesions situated in a previously irradiated area are considered measurable if progression has been demonstrated in such lesions.
7. Have provided archival tumor tissue sample or newly obtained core or excisional biopsy of a tumor lesion not previously irradiated. Formalin-fixed, paraffin embedded (FFPE) tissue blocks are preferred to slides. Newly obtained biopsies are preferred to archived tissue.

8. Have an Eastern Cooperative Oncology Group (ECOG) performance status of 0 to 1. Evaluation of ECOG is to be performed prior to the first dose of treatment.
9. Patient's life expectancy ≥ 16 weeks.
10. Have adequate organ function as defined in the following table (Table 1). Specimens must be collected within 10 days prior to the start of study treatment. Before patients can be enrolled, they must have normal laboratory values as outlined in Table 1. Labs must also fall within normal limits prior to infusion.

Table 1 Adequate Organ Function Laboratory Values

System	Laboratory Value
Hematological	
Absolute neutrophil count (ANC)	$\geq 1500/\mu\text{L}$

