6.1.3 Laboratory Procedures/Assessments

Details regarding specific laboratory procedures/assessments to be performed in this trial are provided below.

Laboratory tests for hematology, chemistry, urinalysis, and others are specified in Table 9.

Table 9 Laboratory Tests

Hematology	Chemistry	Urinalysis	Other
Hematocrit	Albumin	Blood	Serum β -human chorionic gonadotropin†
Hemoglobin	Alkaline phosphatase	Glucose	(β -hCG)†
Platelet count	Alanine aminotransferase (ALT)	Protein	PT (INR)
WBC (total and differential)	Aspartate aminotransferase (AST)	Specific gravity	aPTT
Red Blood Cell Count	Lactate dehydrogenase (LDH)	Microscopic exam (If abnormal)	Total triiodothyronine (T3)
Absolute Neutrophil Count	Carbon Dioxide ‡	results are noted	Free tyroxine (T4)
Absolute Lymphocyte Count	(CO_2 or bicarbonate)	Urine pregnancy test †	Thyroid stimulating hormone (TSH)
	Uric Acid		PK
	Calcium		
	Chloride		Stools for correlative studies
	Glucose		
	Phosphorus		
	Potassium		
	Sodium		
	Magnesium		
	Total Bilirubin		
	Direct Bilirubin (If total bilirubin is elevated above the upper limit of normal)		
	Total protein		
	Blood Urea Nitrogen		

† Perform on women of childbearing potential only. If urine pregnancy results cannot be confirmed as negative, a serum pregnancy test will be required.

‡ If considered standard of care in your region.

Table 10 Laboratory safety variables

Haematology/Haemostasis (whole blood)	Clinical Chemistry (serum or plasma)
B-Hemoglobin (Hb)	S/P-Creatinine
B-Leukocyte count	S/P-Bilirubin, total
B-Absolute neutrophil count	S/P-Alkaline phosphatase (ALP)
B-Absolute lymphocyte count	S/P-Aspartate transaminase (AST)
B-Platelet count	S/P-Alanine transaminase (ALT)
B-Mean cell volume (MCV)	S/P-Albumin
	S/P-Potassium
	S/P-Calcium, total
	S/P-Sodium
Urinalysis (dipstick)	S/P-Urea or Blood Urea Nitrogen (BUN)
U-Hb/Erythrocytes/Blood	S/P-Total Protein
U-Protein/Albumin	
U-Glucose	

NB. In case a patient shows an AST **or** ALT $\geq 3 \times \text{ULN}$ together with total bilirubin $\geq 2 \times \text{ULN}$ please refer to Appendix E ‘Actions required in cases of increases in liver biochemistry and evaluation of Hy’s Law’, for further instructions.

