- All AEs meeting serious criteria, from the time of intervention allocation/randomization through 90 days following cessation of study intervention or 30 days following cessation of study intervention if the participant initiates new anticancer therapy, whichever is earlier, must be reported by the investigator.
- All pregnancies and exposure during breastfeeding, from the time of intervention allocation/randomization through 120 days following cessation of study intervention, or 30 days following cessation of study intervention if the participant initiates new anticancer therapy must be reported by the investigator.
- Additionally, any SAE brought to the attention of an investigator at any time outside of the time period specified above must be reported immediately to Merck if the event is considered drug-related.

Investigators are not obligated to actively seek AEs or SAEs or other reportable safety events in former study participants. However, if the investigator learns of any SAE, including a death, at any time after a participant has been discharged from the study, and he/she considers the event to be reasonably related to the study intervention or study participation, the investigator must promptly notify Merck.

All initial and follow-up AEs, SAEs, and other reportable safety events will be recorded and reported to Merck within the time frames as indicated in Table 11.

Table 11 Reporting Time Periods and Time Frames for Adverse Events and Other Reportable Safety Events

Type of Event	Reporting Time Period: Consent to Randomization/Allocation	Reporting Time Period: Randomization/Allocation through Protocol-specified Follow-up Period	Reporting Time Period: After the Protocol-specified Follow-up Period	Time Frame to Report Event and Follow-up Information to Merck:
Serious Adverse Event (SAE) including Cancer and Overdose	Report if: - due to protocol-specified intervention - causes exclusion - participant is receiving placebo run-in or other run-in treatment	Report all	Report if: - drug/vaccine related. (Follow ongoing to outcome)	Within 2 business days but no longer than 3 calendar days of learning of event
Pregnancy/Lactation Exposure	Report if: - due to intervention - causes exclusion	Report all	Previously reported – Follow to completion/termination; report outcome	Within 2 business days but no longer than 3 calendar days of learning of event

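### Appendix 3 states a 1-month minimum for contraception after the last dose where inclusion criterion 3b requires 120 days, and it leaves its two rules on method unreconciled

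*Combined protocol and SAP*

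**What the plan says.** **Duration.** Section 5.1.1, inclusion criterion 3b, admits a woman of childbearing potential who agrees to follow Appendix 3 "during the treatment period and for at least 120 days after the last dose of study treatment". Section 5.1.2, exclusion criterion 23, uses the same 120-day horizon for women who expect to conceive. Section 6.2.1 collects pregnancies "through 120 days following cessation of study intervention, or 30 days following cessation of study intervention if the participant initiates new anticancer therapy".

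Appendix 3 gives a different figure. Under Acceptable Birth Control Methods, sexually active women "must agree to the use of TWO highly effective forms of contraception in combination", starting at consent, through treatment and "for at least 1 month after last dose of study drug(s"; true abstinence is the alternative. The abstinence entry repeats the 1-month minimum but also requires abstinence for the whole trial.

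**Method.** Under Contraception Requirements, Appendix 3 makes women of childbearing potential eligible if "they agree to use a highly effective method of contraception that has a low user dependency consistently and correctly as described in Table 9" and "during the protocol-defined time frame". Table 9 is "Table 9 Laboratory Tests". The list that fits the description is "Table 16 Highly-Effective Contraceptive Methods That Have Low User Dependency", in the appendix itself. Between that requirement and Table 16, the appendix lists acceptable methods under non-hormonal and hormonal headings. Note b to Table 16 still has a bracketed placeholder where a number of days belongs.

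**The concern.** Criterion 3b delegates the practical detail to Appendix 3, so the appendix is what a site is likely to have open when it counsels a patient. The only number there is the shorter one. The same document assigns olaparib a medium to high fetal risk (Appendix 3) and warns that pembrolizumab may harm a fetus (Section 5.1.3.2). If the appendix is used alone, contraception could stop about three months before the protocol's own criteria allow.

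The method rules raise a different problem. A woman using a combined pill plus condom is acceptable on the appendix list but does not use a Table 16 method. Section 5.1 permits no exceptions to eligibility and Section 2.1 describes a multi-center trial, so two sites could reach opposite decisions on the same woman. The cross-reference that should settle the matter leads to laboratory tests.

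**Working it through.** The plan has no calculated figure to reproduce here. The check compares stated periods and matches two lists.

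**Step 1: durations side by side**

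| Place | Minimum after last dose |
|---|---|
| 5.1.1, inclusion 3b | 120 days |
| 5.1.2, exclusion 23 | 120 days |
| 6.2.1, pregnancy reporting | 120 days (30 if new anticancer therapy starts) |
| Appendix 3, two-method rule | 1 month |
| Appendix 3, abstinence entry | 1 month, plus the whole trial |
| Appendix 3, Table 16 note b | blank |

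The shorter branch in 6.2.1 concerns reporting only. Criterion 3b has no such branch.

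**Step 2: gap between the two minimums.** A month is taken as 28 to 31 days.

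- 120 − 31 = 89 days
- 120 − 28 = 92 days

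This applies to the two-method rule only. The abstinence entry is not a clean 1-month minimum, because it adds the whole trial and Table 16 ties abstinence to the full period of risk. Its end date is unclear rather than plainly short.

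**Step 3: does the 1-month rule belong to one drug only?** The section opens with olaparib, which might suggest an olaparib-only rule beside a pembrolizumab rule. The sentence itself refers to study drug with an optional plural and names neither agent, so the text does not limit it that way.

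**Step 4: accepted options matched to Table 16.** Every listed option except abstinence is paired with a male condom, which is not in Table 16.

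| Accepted option | In Table 16? |
|---|---|
| True abstinence | yes |
| Vasectomised partner | yes |
| Tubal occlusion | yes |
| IUD | yes |
| Implant | yes |
| Hormonal intrauterine system | yes |
| Combined pill | no |
| Desogestrel pill | no |
| Hormonal injection | no |
| Transdermal system | no |
| Intravaginal device | no |

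Non-hormonal plus hormonal: 4 + 7 = 11. In Table 16: 6. Not in Table 16: 11 − 6 = 5, all hormonal. If abstinence is treated as an alternative to the list rather than an item on it, the count is 5 of 10, with the same five options.

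**The case against.** The strongest reply is that the durations do not conflict. Each is a minimum, and 120 days satisfies both. Criterion 3b states 120 days in the same sentence that points to the appendix, exclusion 23 repeats that horizon, and the appendix defers to a time frame set by the protocol. This stands. A reader might infer that the protocol releases women from contraception after one month. It does not: read as a whole, it requires 120 days. What remains is that the document sites are sent to shows only the lower figure.

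On method, the two rules can be applied together: a Table 16 method plus a second form. That reading is available, but the text does not state it, and it sits badly with a list that calls five non-Table 16 options acceptable. A reader might infer instead that the five must be deleted. The documents do not support that either, since they do not show which rule the sponsor intended. Dropping the low-user-dependency condition would resolve the mismatch equally well, and each of the five already carries a condom.

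The blank in note b has little demonstrated effect. The note applies only where an interaction may weaken hormonal contraception. Table 7 lists hormonal contraceptives among the CYP3A4 substrates whose exposure olaparib may increase, and the appendix list already pairs every hormonal method with a condom.

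Finally, 5 of 11 counts entries in a list, not women. The protocol does not say how many of the 48 patients will be of childbearing potential, and Appendix 3 removes several groups from that category, including women with a hysterectomy or with radiation- or chemotherapy-induced menopause of more than a year.

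**Conclusion.** The inconsistency is real and should be corrected; it is one of safety guidance and eligibility wording. The appendix's two-method minimum falls 89 to 92 days short of the period in criterion 3b, and the appendix never states that period. The risk is that a site relies on the appendix alone; a site that follows 3b meets both minimums.

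Separately, the low-user-dependency condition cites the wrong table, and five of the 11 accepted options (five of 10 without abstinence) are absent from the right one, with no statement on whether the two rules are cumulative.

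Several things cannot be concluded. The documents do not show which interval is pharmacologically necessary, so this is not a finding that one month is too short in itself. The consent text was not available, so whether it repeats the shorter figure is unknown. The number of women affected cannot be estimated. No endpoint, sample size or analysis is affected.

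**What to change.** 1. In both the two-method sentence and the abstinence entry of Appendix 3, replace the 1-month period with at least 120 days after the last dose of either study drug, whichever is later. The last clause matters because Section 2.0 lets some patients continue pembrolizumab alone, so the two last doses may fall on different dates.
2. Under Contraception Requirements, change the reference from Table 9 to Table 16.
3. Fill the blank in Table 16 note b with a period of at least 120 days.
4. State one method rule. Either require a Table 16 method plus male condom (or true abstinence), or drop the low-user-dependency condition and keep the existing list of accepted options. The choice is the sponsor's.
5. Check that the consent text gives the same period and method rule.

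The cost is wording in one appendix and the consent check, with no added visits, tests or patients. Under the first choice in item 4, women who use only one of the five unlisted methods would have to change method or abstain to be eligible; the second choice avoids that.
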